11.2 Statistical Design

Part a. Lead-in phase

The MTD is defined as the highest dose level with ≤ 1 out of 6 patients experience a DLT during the first 28 days of treatment. DLT is defined in section 5.2.2. The dosing schema for the combination treatment during the lead in phase is shown in Table 1 in section 5.2.1.

Part b. Phase II

Historical data on similar patients shows an ORR of 10-15%. The target ORR with the experimental treatment is 30%. This regimen of the combination treatment will be considered worthy of further investigation if it elicits an increase in ORR to 30% with acceptable toxicity. A $>30\%$ drug-related grade 3/4 toxicity rate is considered unacceptable. Thus, interim monitoring rules, assuming the prior distributions above, were constructed that meet the following two conditions,

- 1) Stop if $\text{Prob}\{p(\text{ORR}, E) < p(\text{ORR}, H) + 0.15 \mid \text{data}\} > 0.975$, or
- 2) Stop if $\text{Prob}\{p(\text{TOX}, E) > 0.30 \mid \text{data}\} > 0.975$,

where $P(\text{ORR}, E)$ and $P(\text{TOX}, E)$ are the true ORR and toxicity rates for the combination treatment, and $p(\text{ORR}, H)$ is the true ORR rate of the standard treatment. The first rule provides for stopping the study if the data suggest that it is unlikely (i.e., probability $< 2.5\%$) that ORR rate of the combination treatment is greater than the ORR rate of standard treatment by 15.0%. The second condition will stop the study early if excessive therapy-related grade 3/4 toxicity ($>30\%$) is highly probable (i.e., probability $>97.5\%$) for the combination treatment. Monitoring for toxicity and futility will not begin until 5 patients have been evaluated, and cohort size for future evaluations is 5.

The monitoring rule for the toxicity rate, based on these assumptions and monitoring conditions above is found in Table 4. **For example, accrual will cease if 4 or more patients experience toxicities among the first 5 patients.**

Table 4. Stop accrual if the number of drug-related grade 3/4 toxicities is greater than or equal

to indicated (i.e., # patients with toxicities) among the number of patients evaluated								
# patients evaluated	5	10	15	20	25	30	35	40
# patients with toxicities	4-5	6-10	8-15	10-20	12-25	14-30	16-35	Always stop with this many patients

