Monitoring the ORR rate, based on the above assumptions and monitoring conditions is found in Table 5. **For example, accrual will cease if less than 2 patients experience an overall response within 3 months of initiation of therapy in the first 10 patients treated.**

Table 5. Stop accrual if the number with overall response is less than or equal to indicated (i.e., # patients with overall response) among the number of patients evaluated					
# patients evaluated	5	10-15	20-25	30-35	40
# patients with overall response	Never stop with this many patients	0-1	0-2	0-3	Always stop with this many patients

Multic Lean Desktop (version 2.1.0) was used to generate the toxicity and futility stopping boundaries and the OC table (Table 6). In order to utilize the software for the design, a beta (0.3, 1.7) and beta (0.4, 1.6) priors were assumed for the standard treatment response distribution and experimental treatment response prior distribution, respectively. In addition, a 30% toxicity constant rate and beta (0.6, 1.4) priors were assumed for the standard treatment toxicity constant rate and experimental treatment toxicity prior distribution, respectively.

The probability of stopping the study early if the true ORR of the combination treatment was 30% and the true toxicity rate was 30% was 15.1%. Probabilities of stopping early for high true toxicity rates (i.e., 50%) were 84.0% when the true ORR was 30% and 83.6% when true ORR rate was 40%.

Table 6. Operating characteristics for simultaneous monitoring response and toxicity rates for patients treated with combination treatment		
True Toxicity Rate	True ORR	Prob(stop the trial early)
0.10	0.15	0.3001
	0.20	0.1479
	0.25	0.0703
	0.30	0.0328

Table 6. Operating characteristics for simultaneous monitoring response and toxicity rates for patients treated with combination treatment

True Toxicity Rate	True ORR	Prob(stop the trial early)
	0.35	0.0151
	0.40	0.0069
0.20	0.15	0.3101
	0.20	0.1601
	0.25	0.0836
	0.30	0.0466
	0.35	0.0292
	0.40	0.0211
0.30	0.15	0.3859
	0.20	0.2523
	0.25	0.1842
	0.30	0.1514
	0.35	0.1358
	0.40	0.1286
0.40	0.15	0.6194
	0.20	0.5367
	0.20	0.4945
	0.30	0.4741
	0.35	0.4645
	0.40	0.4600
0.50	0.15	0.8841
	0.20	0.8589
	0.25	0.8460
	0.30	0.8398
	0.35	0.8369
	0.40	0.8355

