12.0 PROTOCOL ADMINISTRATION

This study will be monitored by the MD Anderson IND Office and a protocol-specific monitoring plan will be followed.

Protocol amendments

Changes to the protocol will be made only when protocol amendments have been signed by the principal investigator and approved by the sponsor and the IRB of the study center.

Archival of data

All patient data (including source data) generated in connection with this study will be kept in the archives of the MDACC for at least 15 years after the study has been completed. All data will be available for inspection by company representatives of the Medical Department and by regulatory authorities.

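### Six of the seven toxicity stopping boundaries in Table 4 do not meet the stated 0.975 cutoff under the stated prior, so the quoted stopping probabilities do not describe the written rule

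*Combined protocol and SAP*

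**What the plan says.** All of this is in section 11.2 (Statistical Design, Part b) of the combined protocol and SAP.

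- **Rule 1 (futility):** stop if the posterior probability that the combination's ORR is below the standard ORR plus 0.15 exceeds 0.975.
- **Rule 2 (toxicity):** stop if the posterior probability of a toxicity rate above 0.30 exceeds 0.975. The text repeats this in words: "The second condition will stop the study early if excessive therapy-related grade 3/4 toxicity" above 30% is highly probable, glossed as a probability over 97.5%.
- **Toxicity inputs:** "a 30% toxicity constant rate and beta (0.6, 1.4) priors were assumed" for the standard and experimental treatment respectively.
- **Response priors:** Beta(0.3, 1.7) for the standard and Beta(0.4, 1.6) for the experimental treatment.
- **Looks:** every 5 patients from 5 onward, to a maximum of 40.
- **Table 4 (toxicity):** stop at 4/5, 6/10, 8/15, 10/20, 12/25, 14/30 or 16/35 and above. Of its origin the text says: "The monitoring rule for the toxicity rate, based on these assumptions and monitoring conditions above is found in Table 4".
- **Table 5 (futility):** stop at 0-1 responders among 10-15 patients, 0-2 among 20-25 and 0-3 among 30-35. Its example says "accrual will cease if less than 2 patients experience an overall response within 3 months of initiation of therapy" among the first 10.
- **Table 6 and text:** early stopping is 15.1% at true ORR 30% and toxicity 30%. At 50% toxicity it is 84.0% (ORR 30%) and 83.6% (ORR 40%).

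The boundaries and Table 6 are attributed to the same software.

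**The concern.** Table 4 is presented as derived from rule 2. If it is not, the formula and the table conflict at 6/10, 8/15, 10/20, 12/25, 14/30 and 16/35: the table says stop and the formula says continue. The protocol gives no order of precedence. The only worked toxicity example, 4 of 5, is the one boundary where the two agree, so the example does not expose the conflict.

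These are the only numerical stopping boundaries for phase II. The quoted operating characteristics are what a review board relies on to judge the protection against excess toxicity, so it matters which rule they describe.

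**Working it through.** **1. Toxicity posterior at each boundary.** With t toxicities in n patients the posterior is Beta(0.6 + t, 1.4 + n − t), and the quantity compared with 0.975 is 1 − BetaCDF(0.30; 0.6 + t, 1.4 + n − t).

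| n | Table 4 boundary | Posterior one patient below | Posterior at boundary | Above 0.975? | Boundary at 0.975 |
|---|---|---|---|---|---|
| 5 | 4 | .8745 | .9751 | yes | 4 |
| 10 | 6 | .8798 | .9625 | no | 7 |
| 15 | 8 | .8927 | .9597 | no | 9 |
| 20 | 10 | .9059 | .9608 | no | 11 |
| 25 | 12 | .9180 | .9634 | no | 13 |
| 30 | 14 | .9286 | .9666 | no | 15 |
| 35 | 16 | .9379 | .9699 | no | 17 |

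One more event at the six failing looks gives .9857 to .9914. Under the stated prior, Table 4 fits any cutoff from about .938 (largest value one below) to just under .9597 (smallest value at a boundary).

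**2. Reproducing Table 6.** The binomial counts were carried forward exactly over looks at 5, 10, ..., 35, with response and toxicity independent, so that

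P(stop early) = 1 − [1 − P(stop for toxicity)] × [1 − P(stop for futility)].

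With Table 4 held fixed, 792 non-decreasing futility boundary sets were searched. Only one reproduces all 30 cells (largest difference .00005, reading the second 0.20 row at toxicity 0.40 as ORR 0.25): stop at 0 responders among 10-15, at most 1 among 20-25, and at most 2 among 30-35. Toxicity stopping under Table 4 is .1231 at a true rate of 30% and .8345 at 50%. Futility stopping under those bounds is .0323 at ORR 30% and .0063 at ORR 40%.

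- 30%/30%: 1 − .8769 × .9677 = .1514 (quoted 15.1%)
- toxicity 50%, ORR 30%: 1 − .1655 × .9677 = .8398 (quoted 84.0%)
- toxicity 50%, ORR 40%: 1 − .1655 × .9937 = .8355 (quoted 83.6%)

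The calculation therefore matches the software. The quoted figures belong to Table 4 paired with futility bounds one responder lower than Table 5 prints. Tables 4 and 5 exactly as printed give 26.1%, 86.1% and 84.2%.

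**3. The rules as written.** For futility, P(pE < pH + 0.15) was integrated over the two response distributions: .9813 at 0/10, .8512 at 1/10, .9707 at 1/20, .9716 at 2/30 and .9539 at 3/35. At 0.975 this gives at most 0 among 10-20, at most 1 among 25-30 and at most 2 at 35. Combined with the 0.975 toxicity boundaries:

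| True toxicity / ORR | Quoted | Both rules at 0.975 | Difference (points) |
|---|---|---|---|
| 30% / 30% | 15.1% | 9.1% | 6.0 |
| 50% / 30% | 84.0% | 72.9% | 11.1 |
| 50% / 40% | 83.6% | 72.3% | 11.3 |

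Toxicity rule alone:

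| True toxicity | Table 4 | 0.975 boundaries |
|---|---|---|
| 30% | 12.3% | 6.4% |
| 40% | 45.7% | 30.9% |
| 50% | 83.5% | 72.1% |

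**4. What could have been entered.** The futility bounds behind Table 6 need a cutoff from .9539 to just under .9707. If one cutoff served both rules, it lies between about .954 and .960. Alternatively, the toxicity parameters may have been reversed: Beta(1.4, 0.6) at 0.975 also gives 4, 6, 8, 10, 12, 14, 16. That alone does not explain Table 6. Table 4 with futility bounds at 0.975 gives 24.8% at toxicity 10% and ORR 15%, where Table 6 prints 30.0%.

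**The case against.** The strongest reply is that Table 4 is an explicit count table which staff can follow without computing a posterior. It stops at the same count or one patient sooner than the formula, never later. On that reading the 11-point gap is not a loss of protection; it appears only if someone sets the table aside and applies the formula. This stands, and it limits the practical harm. It does not remove the error: if the table governs, the stated 97.5% certainty is wrong at six looks; if the formula governs, the quoted stopping probabilities are wrong.

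A second reply is that the fault may be a misprinted toxicity prior. If so, the three quoted figures are nearly right for a 0.975 rule: Table 4 with 0.975 futility bounds gives 14.9%, 83.9% and 83.6%. This also stands as a possibility, so the 6- and 11-point gaps depend on the stated prior being the intended one. It still leaves Table 6 unexplained at low ORR, and Table 5 in conflict with every cutoff considered here: its own example, 1 of 10, has a futility posterior of only .851.

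Third, the .954-.960 range assumes one cutoff for both rules. Separate cutoffs, such as 0.95 for toxicity and 0.96 for futility, reproduce Tables 4 and 6 equally well. The range is an inference, not a finding about what was run.

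**Conclusion.** The concern holds. Under the stated prior and constant 30% rate, six of the seven Table 4 boundaries fall short of 0.975 by about 0.005 to 0.015, which is one patient at each look and always towards earlier stopping. For the rules as written, the quoted probabilities overstate early stopping by 6 points at 30% toxicity with 30% ORR, and by about 11 points at 50% toxicity.

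The boundary result is a direct Beta tail calculation. The stopping probabilities also assume looks every 5 patients through 35 and independence of response and toxicity; both are supported by the reproduction of all 30 Table 6 cells. Which input was misreported cannot be settled from the documents. The point should be corrected, but it does not show that the tabulated toxicity rule is too lenient relative to the stated one.

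**What to change.** First retrieve the priors and cutoffs actually entered in the software. Then make rules 1 and 2, their verbal glosses (below 2.5%, above 97.5%), the prior statement and Tables 4, 5 and 6 agree. The documents do not show which route was intended:

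- **(a) Keep Tables 4 and 6.** State the cutoff or cutoffs that generated them. A common 0.955 is one value that reproduces both under the stated priors, subject to confirmation. Correct Table 5 to 0 among 10-15, 0-1 among 20-25 and 0-2 among 30-35, and change its example to match. The stated posterior certainty then falls, to about 95.5% if 0.955 is confirmed.
- **(b) Keep 0.975 and the stated priors.** Reissue Table 4 as 4, 7, 9, 11, 13, 15, 17. Reissue Table 5 as 0 among 10-20, 0-1 among 25-30 and 0-2 at 35, with its example. Reissue Table 6 and the quoted probabilities. The stated chance of stopping at 50% toxicity falls to about 73% at ORR 30%.
- **(c) If the inputs show a different prior,** correct the prior statement and re-derive the same tables.

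In each case relabel the second 0.20 row at toxicity 0.40 in Table 6; its value matches ORR 0.25.

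The cost is a protocol amendment. Section 12.0 says "Changes to the protocol will be made only when protocol amendments have been signed by the principal investigator"; agreement from the IRB and the sponsor is required as well. Routes (b) and (c) also need a software rerun.

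### Table 5's futility boundaries cannot produce Table 6: at the 30% target ORR they stop early in 26.1% of trials, not the quoted 15.1%, and the stated 0.975 cutoff gives neither set

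*Combined protocol and SAP*

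**What the plan says.** All of the following is in section 11.2, Part b.

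- **Rule.** Accrual stops for futility if the posterior probability that the combination's ORR is below the standard ORR plus 0.15 exceeds 0.975. It stops for toxicity if the posterior probability of a grade 3/4 drug-related toxicity rate above 0.30 exceeds 0.975.
- **Looks.** "Monitoring for toxicity and futility will not begin until 5 patients have been evaluated, and cohort size for future evaluations is 5". The maximum is 40 patients (section 11.1).
- **Table 4 (toxicity).** Stop at 4/5, 6/10, 8/15, 10/20, 12/25, 14/30 or 16/35, or more.
- **Table 5 (response).** The heading reads "Stop accrual if the number with overall response is less than or equal to indicated". The cells are 0-1 at 10-15 patients, 0-2 at 20-25 and 0-3 at 30-35, with no stop at 5. The worked example is that "accrual will cease if less than 2 patients experience an overall response within 3 months of initiation of therapy in the first 10 patients".
- **Priors.** Response: beta(0.3, 1.7) for standard and beta(0.4, 1.6) for experimental. Toxicity: beta(0.6, 1.4) for experimental, against a constant 30%.
- **Software.** One program "was used to generate the toxicity and futility stopping boundaries and the OC table (Table 6").
- **Operating characteristics.** The probability of stopping early "if the true ORR of the combination treatment was 30% and the true toxicity rate was 30% was 15.1"%. With toxicity at 50% it is 84.0% (ORR 30%) and 83.6% (ORR 40%).

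**The concern.** If one run of one program produced the boundaries and Table 6, then putting the printed boundaries through the stated looks should return Table 6, and the stated cutoff and priors should return the boundaries. Neither happens.

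Table 5 and its example are what the trial team would apply. With one responder among the first ten patients, the printed rule closes accrual, whereas the rule that fits Table 6 continues. Anyone who judged the design by Table 6 judged a more lenient futility rule than the one written down. The consequence depends on the true rate: the printed rule abandons a regimen at the 30% target more often than stated, and also drops a 15% regimen more often than stated.

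**Working it through.** **Method.** Exact binomial recursion over looks at 5, 10, ..., 35, adding five patients at a time and removing paths that hit a boundary. A stop at 40 is not early. Response and toxicity are taken as independent, so

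P(stop) = 1 − [1 − P(response stop)] × [1 − P(toxicity stop)].

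**Step 1: the components.**

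Table 4 alone stops with probability 0.0006, 0.0149, 0.1231, 0.4566 and 0.8345 at true toxicity 0.10, 0.20, 0.30, 0.40 and 0.50.

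| True ORR | 0.15 | 0.20 | 0.25 | 0.30 | 0.35 | 0.40 |
|---|---|---|---|---|---|---|
| Table 5 as printed (1, 2, 3) | 0.6225 | 0.4193 | 0.2637 | 0.1569 | 0.0885 | 0.0471 |
| One response lower (0, 1, 2) | 0.2997 | 0.1474 | 0.0698 | 0.0323 | 0.0145 | 0.0063 |

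**Step 2: reproduce the quoted 15.1% (ORR 30%, toxicity 30%).**

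- Lowered boundaries: 1 − (1 − 0.0323)(1 − 0.1231) = 0.1514, which is the Table 6 entry.
- Printed boundaries: 1 − (1 − 0.1569)(1 − 0.1231) = 0.2607.

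**Step 3: the rest of Table 6.** The printed boundaries match 0 of 30 cells (largest gap 0.323). The lowered boundaries match 30 of 30 (largest gap 0.00005), reading the second row labelled 0.20 under toxicity 0.40 (entry 0.4945) as ORR 0.25. Shifting the three boundary pairs separately by −1, 0 or +1 gives 27 combinations. Only the uniform −1 shift fits; the next best misses by 0.104.

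At ORR 30%:

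| True toxicity | Printed Table 5 | Table 6 |
|---|---|---|
| 10% | 0.1574 | 0.0328 |
| 20% | 0.1694 | 0.0466 |
| 30% | 0.2607 | 0.1514 |
| 40% | 0.5418 | 0.4741 |
| 50% | 0.8605 | 0.8398 |

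Most of the gap arises at the look at 10. With a true rate of 0.30, P(0 or 1 of 10) = 0.7^10 + 10 × 0.3 × 0.7^9 = 0.149, against P(0 of 10) = 0.7^10 = 0.028.

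**Step 4: do the boundaries follow from 0.975?** The response posterior is P(pE < pH + 0.15), with pE ~ beta(0.4 + r, 1.6 + n − r) and pH ~ beta(0.3, 1.7), by numerical integration.

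| n | Printed boundary | Posterior | Lowered boundary | Posterior |
|---|---|---|---|---|
| 10 | 1 | 0.8512 | 0 | 0.9813 |
| 15 | 1 | 0.9342 | 0 | 0.9936 |
| 20 | 2 | 0.8936 | 1 | 0.9707 |
| 25 | 2 | 0.9445 | 1 | 0.9869 |
| 30 | 3 | 0.9184 | 2 | 0.9716 |
| 35 | 3 | 0.9539 | 2 | 0.9857 |

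No printed boundary reaches 0.975. The lowered set misses it at 1/20 and 2/30.

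For Table 4, P(pT > 0.30) with pT ~ beta(0.6 + t, 1.4 + n − t) is 0.9751 at 4/5, then 0.9625, 0.9597, 0.9608, 0.9634, 0.9666 and 0.9699 at 6/10 to 16/35. Only the first look passes.

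**Step 5: which cutoffs would work?** The lowered response set needs a cutoff from 0.9539 to just under 0.9707. Table 4 needs one from 0.9379 to just under 0.9597. A common value must lie from 0.9539 to just under 0.9597. No single cutoff gives the printed Table 5 with a look at 5: stopping at 1/10 needs a cutoff below 0.8512, while not stopping at 0/5 needs at least 0.9384.

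A literal 0.975 gives response boundaries 0, 0, 0, 1, 1, 2 at n = 10 to 35 and toxicity boundaries 4, 7, 9, 11, 13, 15, 17 at n = 5 to 35. The three quoted probabilities would then be 9.1%, 72.9% and 72.3%.

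**The case against.** The arithmetic is not in dispute, and no reading rescues the text. A strict less-than reading of Table 5 would fit Table 6, but the heading, the cells and the worked example all include one response in ten. Several limits on the finding are fair:

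- **Table 6 does not identify every boundary.** Removing the lowered boundaries at 15, 25 and 35 leaves all 30 cells unchanged. Table 6 therefore fixes those at 10, 20 and 30; the others are inferred from Table 5's paired columns.
- **The narrow cutoff window assumes one cutoff for both rules.** The text prints 0.975 for both, but they are separate conditions and the software settings are not given.
- **The effect is uneven.** Of the three probabilities quoted in the text, only 15.1% moves materially. The other two become 86.1% (from 84.0%) and 84.2% (from 83.6%), because toxicity stopping dominates there.
- **The printed rule has a merit.** It stops an inactive regimen more often. The documents do not show which set was intended.
- **The primary analysis does not use the boundaries in its calculation.** It is an ORR estimate with a 95% confidence interval.

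These points qualify how the finding is stated. They do not remove the contradiction between the decision rule and its reported performance.

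**Conclusion.** The concern holds. Table 5 and its example stop at one more response than the boundaries behind Table 6. At the 30% target, early stopping is 15.7% rather than 3.3% at toxicity 10% (4.8 times), and 26.1% rather than 15.1% at toxicity 30% (1.7 times). At ORR 40% and toxicity 10% it is 4.8% against 0.7%. At ORR 15% and toxicity 10% it is 62.3% against 30.0%. Separately, the 0.975 cutoff with the stated priors gives neither response set, and gives Table 4 only at its first entry, so the text of the rule cannot decide between the tables.

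The result rests on looks every five patients and on independence of response and toxicity. The plan does not state independence, but the match in all 30 cells supports it. This must be corrected, because a stated stopping rule and its stated operating characteristics are incompatible.

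**What to change.** Decide which rule is intended. Then regenerate the cutoff text, Tables 4 and 5, the worked example, Table 6 (including the duplicated 0.20 label) and the three quoted probabilities from one software run, and report the settings. There are three coherent routes, and the choice is the sponsor's:

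- **(a) Keep Table 6.** Table 5 becomes 0 at 10-15, 0-1 at 20-25 and 0-2 at 30-35. The example becomes no responders among the first ten. The 0.975, 97.5% and 2.5% in the text are replaced by the cutoff actually used, which must lie from 0.9539 to just under 0.9597 if one value serves both rules. This is the smallest edit. Its cost is that a 15% regimen is stopped in 30.0% of trials at toxicity 10%, not the 62.3% of printed Table 5.
- **(b) Keep 0.975.** Recompute all three tables; the boundaries and quoted probabilities become those at the end of the working. The cost is that early stopping at toxicity 50% and ORR 30% falls from 84.0% to 72.9%.
- **(c) Keep Table 5.** Replace Table 6, and change the quoted figures to 26.1%, 86.1% and 84.2%. State the response rule as fixed boundaries with a first response look at 10, since no single cutoff yields them. Even without the look at 5, 3/25 (0.860) and 4/35 (0.894) do not stop while 1/10 (0.851) does. The cost is the higher chance of stopping at the 30% target.

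Each route changes text and tables only; none adds patients.

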11.1 Sample Size

Part a. Lead-in phase

The primary objective of the lead-in phase is to determine the safety of lirilumab in combination with 5-azacytidine in patients with refractory/ relapsed AML. Up to 24 patients will be accrued into lead-in part of the study.

Part b. Phase II

Up to 40 patients (including 6 patients treated at the MTD from the lead-in part) will be recruited for the Phase II part.

The primary objective of the phase II is to determine the efficacy of lirilumab in combination with 5-azacytidine in patients with refractory, relapsed or untreated AML. The efficacy of the combination will be measured by the overall response rate (ORR), defined as CR (complete remission) + CRp (complete remission with incomplete platelet recovery) + CRi (complete remission with incomplete count recovery) + PR (partial response) + marrow clearance of blasts + HI (Hematological improvement) within 3 months of treatment initiation among adult patients with refractory/ relapsed AML. ORR and toxicity will be monitored simultaneously using the Bayesian approach of Thall, Simon, Estey (1995, 1996) and the extension by Thall and Sung (1998).

Once safety of the MTD has been established, any patients still on study at a dose lower than MTD can be dose escalated up to MTD. Patients treated in the lead-in phase at MTD will be included in the phase II portion of the study.

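### The historical response prior, Beta(0.3, 1.7), has a plausible mean but the weight of two patients, which leaves futility rule 1 as written with little power; Table 5 as printed does not share that weakness, but does not follow from the rule

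*Combined protocol and SAP*

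**What the plan says.** On the benchmark, section 11.2 states "Historical data on similar patients shows an ORR of 10-15"% and "The target ORR with the experimental treatment is 30"%. Section 3.0 gives the same 10-15% range for single-agent hypomethylator therapy. Neither section gives the number of patients behind it.

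Futility rule 1 stops accrual when the posterior probability that the experimental ORR is below the historical ORR plus 0.15 exceeds 0.975. On priors: "a beta (0.3, 1.7) and beta (0.4, 1.6) priors were assumed for the standard treatment response distribution", of which the first is the historical prior and the second the experimental one. On timing: "Monitoring for toxicity and futility will not begin until 5 patients have been evaluated, and cohort size for future evaluations is 5". The maximum comes from section 11.1: "Up to 40 patients (including 6 patients treated at the MTD from the lead-in part) will be recruited for the Phase II part".

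Table 5 prints the resulting limits: no stopping at 5 patients, then stop at 0-1 responses among 10-15 patients, 0-2 among 20-25 and 0-3 among 30-35. Its worked example is that "accrual will cease if less than 2 patients experience an overall response within 3 months of initiation of therapy in the first 10 patients treated". Overall early-stopping probabilities in Table 6 include 0.3001 at true ORR 15% with toxicity 10%, and 0.1514 at ORR 30% with toxicity 30%.

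**The concern.** Rule 1 compares two uncertain rates. The experimental rate is updated by up to 35 patients before the last look. The historical rate has no concurrent arm and keeps its prior throughout, so uncertainty placed on it at the design stage stays in every posterior probability. A near-uninformative prior is reasonable for the experimental arm, where data soon outweigh it. For a fixed benchmark it tells the rule that the historical rate could be almost anything, and poor results then seldom reach 0.975.

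Rule 1 is the plan's only formal rule for lack of efficacy; the final analysis of ORR is an estimate with a confidence interval. If the rule rarely fires, a combination that adds nothing to the hypomethylator alone tends to run to 40 patients.

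**Working it through.** **Inputs.** All are from section 11.2 except the maximum of 40 (section 11.1): priors Beta(0.3, 1.7) and Beta(0.4, 1.6), margin 0.15, cutoff 0.975, looks at 5, 10, ..., 35, and the limits printed in Tables 4 and 5.

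**1. The historical prior.** Its weight is 0.3 + 1.7 = 2 patients and its mean is 0.3/2 = 0.15. The median is 0.05 and the 95% interval is 0.00 to 0.74. The mass is 7% between 0.10 and 0.15, 50% below 0.05 and 19% above 0.30.

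**2. Limits implied by rule 1.** With x responses in n patients, pE ~ Beta(0.4 + x, 1.6 + n - x) and pH ~ Beta(0.3, 1.7). The quantity P(pE < pH + 0.15) is the integral of F_E(h + 0.15) over the density of pH. Values: 0/10 gives 0.981 (stop); 1/10 gives 0.851 (continue); 1/20 gives 0.971 (continue); 1/25 gives 0.987 (stop); 2/30 gives 0.972 (continue); 2/35 gives 0.986 (stop). The rule therefore stops at 0, 0, 0, 1, 1, 2 or fewer responses at n = 10, 15, ..., 35, and never at n = 5.

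**3. Reproducing Table 6.** Let F be the probability of stopping for futility and T for toxicity, each by exact binomial recursion over the looks, with T from Table 4 as printed. If response and toxicity are independent, overall stopping is 1 - (1 - F)(1 - T). T is 0.0006 at toxicity 10% and 0.1231 at 30%.

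- Rule 1 as written: F = 0.248 at ORR 15%, so about 0.248 overall at toxicity 10%, against 0.3001 in Table 6.
- Table 5 as printed: F = 0.6225 at ORR 15%, so 1 - 0.3775 × 0.9994 = 0.623, against 0.3001. At ORR 30% and toxicity 30%, F = 0.1569 gives 1 - 0.8431 × 0.8769 = 0.261, against 0.1514.
- Limits 0, 0, 1, 1, 2, 2, each one response below Table 5: F = 0.2997 gives 1 - 0.7003 × 0.9994 = 0.3001, and F = 0.0323 gives 1 - 0.9677 × 0.8769 = 0.1514. These limits reproduce every cell of Table 6 to four decimals, reading the repeated 0.20 row under toxicity 0.40 as 0.25. They correspond to rule 1 with a cutoff of about 0.96-0.97.

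So rule 1, Table 5 and Table 6 imply three different sets of limits.

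**4. Futility stopping, present and alternative.** The last six rows keep rule 1, cutoff 0.975 and Beta(0.4, 1.6), and change only the historical prior. Its size is an assumption. None of the rows stops at n = 5.

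| Limits from | n = 10, 15, ..., 35 | Stop, ORR 10% | Stop, ORR 15% | Stop, ORR 30% | Expected N, ORR 15% |
|---|---|---|---|---|---|
| Rule 1 as written | 0,0,0,1,1,2 | 49% | 25% | 2.9% | 33.5 |
| Limits behind Table 6 | 0,0,1,1,2,2 | 56% | 30% | 3.2% | 32.4 |
| Table 5 as printed | 1,1,2,2,3,3 | 84% | 62% | 15.7% | 22.3 |
| Size 20, mean 10% | 0,0,1,1,2,3 | 64% | 35% | 3.3% | about 32 |
| Size 20, mean 12.5% | 0,0,1,2,3,3 | 71% | 42% | 3.8% | 30.8 |
| Size 20, mean 15% | 0,1,1,2,3,4 | 81% | 52% | 5.6% | 28.6 |
| Size 100, mean 10% | 0,0,1,2,3,4 | 79% | 48% | 4.1% | 30.5 |
| Size 100, mean 12.5% | 0,1,1,2,3,4 | 81% | 52% | 5.6% | 28.6 |
| Size 100, mean 15% | 0,1,2,3,4,5 | 91% | 67% | 8.4% | 25.7 |

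Over sizes 20 to 1000 and means 10% to 15%, stopping ranges over 35-74% at ORR 15%, 64-93% at 10% and 3-20% at 30%.

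**The case against.** A reader might infer that the prior contradicts the stated history. It does not: its mean of 15% lies within 10-15%. The fault is precision, not location.

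A reader might also infer that, under this plan, most trials of an ineffective combination would run to 40 patients. That is true of rule 1 as written at ORR 15% (75%) and of Table 6 at low toxicity (about 70%). At ORR 10% it is only about half under rule 1 (51%). It is false for Table 5, which is the explicit accrual instruction and has a worked example: 62% of trials stop at 15% and 84% at 10%. Until the plan says which limits govern, the practical effect of the prior is not settled. This objection stands and bounds the point.

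Two further objections have force. Table 6 discloses the 0.3001 openly. And the cutoff matters as well as the prior: with the stated priors, a cutoff of 0.90 stops 59% at ORR 15%. But that costs 18% stopping at 30%, a worse trade than Beta(15, 85) with 67% and 8.4%.

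Finally, Beta(15, 85) is not uniquely right. The documents give no historical sample size, and this prior sits at the upper end of the range, with 46% of its mass in 10-15% and 47% above.

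**Conclusion.** The point holds as a fault of precision. A two-patient prior on a benchmark that is never updated does not represent a 10-15% history, and it is a real cause of the low futility stopping under rule 1 as written and in Table 6. A prior worth only 20 patients with mean 12.5-15% already raises stopping at ORR 15% from 25% to 42-52%, with 4-6% at ORR 30%, so the conclusion does not depend on an assumed size of 100. The low-power finding does not extend to Table 5. The fault there is different: the table cannot be derived from the stated rule and priors (1 of 10 gives 0.851, not above 0.975), does not reproduce Table 6, and stops 16% of trials at the target rate.

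Correcting Table 5 to match rule 1 while keeping this prior would lower stopping at ORR 15% from 62% to 25%, so prior and tables need to be settled together. The figures assume looks at exactly 5, 10, ..., 35 evaluated patients; the overall probabilities also assume independence of response and toxicity.

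**What to change.** Replace Beta(0.3, 1.7) for the historical ORR by an informative prior centred within 10-15%. State the source and number of historical patients and derive the prior's size from them. Keep Beta(0.4, 1.6) for the experimental arm. Rerun the software and reissue rule 1, Table 5 with its worked example, and Table 6 so that all three agree. If the size cannot be documented, show the operating characteristics over a range of sizes.

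The cost is one software rerun and an amendment to section 11.2. Relative to rule 1 as written, stopping at the 30% target rises from 2.9% to about 4-8% for the size-100 examples, and to as much as 20% at the extreme of the range examined. Relative to Table 5 as printed there is a trade: with Beta(15, 85) the expected N at ORR 15% rises from 22.3 to 25.7, in exchange for about half the stopping at 30% (8.4% against 15.7%).
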